7.3 Analysis Populations

All subjects in whom surgery is attempted will be included in both the Intent to Treat (ITT) and in the Safety analysis populations. Effectiveness will also be evaluated using a Per Protocol (PP) analysis set. This set will include subjects with successful implantation, no major protocol deviations, and a non-missing primary effectiveness endpoint. The PP analysis set will be supportive of the ITT findings.

7.4 Sample Size

A sample of 100 eyes provides 94.9% power to reject the null hypothesis that $>10\%$ of eyes will exhibit $>5^\circ$ rotation. We assume that the rotational failure rate will be 2% or less. To allow for losses of 10% per year, a total of up to 124 primary eyes of 124 subjects will be enrolled. If a primary eye of an enrolled subject is explanted during the study, the enrolled fellow eye of that subject may be used in its place for the primary analysis. If the fellow eye was not enrolled or implanted, it may not be used in the primary analysis.

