3.0 STUDY DESIGN

3.1 Description of Study Design

This is a prospective, multicenter, open-label, single arm, post-approval study. A total of 124 subjects (up to 248 eyes, with 124 being primary) who meet all eligibility criteria will be enrolled at 6-8 clinical sites in the United States (US).

It is intended that each enrolled subject will undergo bilateral implantation with the TICL. If only one eye of a given subject meets all of the inclusion and exclusion criteria, or the subject desires surgery in only one eye and that eye meets all of the inclusion and exclusion criteria, then that eye will be the primary eye. If both eyes of a given subject meet all of the inclusion and exclusion criteria, and the subject desires surgery in both eyes, then the eye with the greater magnitude of manifest refraction cylinder will be designated as the primary eye. If both eyes of a given subject meet all of the inclusion and exclusion criteria and the refractive cylinder of the eyes are equal, then the right eye will be designated as the primary eye.

A minimum of 14 subjects requiring a Toric ICL cylinder power of 3.5 or 4.0 D will be enrolled.

Study subjects will be followed at Day 0, Day 1, Week 1, Month 1, 3, 6, 12, 18, and 24 postoperatively (Refer to Appendix A).

STAAR will submit periodic study reports to FDA every six (6) months during the first two (2) years of the study and annually thereafter, unless otherwise specified by FDA. The first report will be submitted 6 months after the initial approval of this study protocol.

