3.2.3 Subject Discontinuation

A subject may be discontinued (at the discretion of the Investigator, the Sponsor and/or the IRB) prior to the final study visit for several reasons, including, but not limited to:

- voluntary withdrawal
- death
- surgical complication preventing implantation of the study lens in any eye
- explant of the study lenses

If both TICL lenses are explanted, a minimum of one post-explant visit should be completed to record safety measures for the subject (e.g., CDVA, cataract/lens evaluation, endothelial cell count, etc.) prior to subject discontinuation.

Prior to discontinuing a subject, every effort should be made to contact the subject, schedule a final study visit, and obtain as much follow-up data as possible.

Adverse events will be followed as described in Section 6.0. Subject withdrawals will be documented clearly on the source document and applicable CRF.

Only subjects who do not receive any study lenses MAY be replaced. Subjects who are discontinued from the study following treatment will not be replaced.

Discontinued subjects should be followed outside of the study protocol according to the Investigator's normal postoperative standard of care.

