6.3 Reporting

6.3.1 On-Site Expedited Reporting

The Investigator is obligated to report the following to the Sponsor within 24 hours of becoming aware of the event to ensure the safety of all participants in the study and to meet regulatory reporting requirements:

- all **SAEs**, regardless of relationship to study device or study protocol
- all **non-serious AEs** determined to be related to the study device (ADE)
- all device malfunctions that do not result in one of the above reportable events
- all secondary surgical interventions (removal, replacement or repositioning) involving the study lens

When reporting these events to the Sponsor, the site should forward any supporting documents along with the appropriate reporting form and the corresponding CRF, if applicable. Refer to the Personnel and Facilities section for Sponsor contact information for reporting of SAEs/ADEs and device malfunctions. Sites must also report applicable events to the reviewing IRB per its established reporting procedures.

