7.2 Study Endpoints

7.2.1 Primary Effectiveness Endpoint

The primary endpoint for this study is rotation of less than or equal to five degrees between 18 and 24 months postoperative. The endpoint will be met if at least 90% of the treated

eyes rotate less than or equal to five degrees between 18 and 24 months postoperative (i.e., $\leq 10\%$ of eyes exhibit $>5^\circ$ rotation).

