7.6 Missing Data Imputation

Missing primary effectiveness endpoint data will be imputed for the primary effectiveness analysis when using the ITT analysis population. The primary method used will be by multiple imputation using SAS PROC MI and MIANALIZE. The method, seed number, number of datasets generated, and predictors to be used will be specified in advance of data lock. Sensitivity analyses will be performed using an imputation of failure (worst case) for all missing and again with an imputation of success for all missing (best case). If the results of the two extreme imputation methods differ in the conclusion drawn, a tipping point analysis will be performed to determine the point at which significance tips.

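### Sections 7.2.1 to 7.6 have no rule that scores a primary eye as a failure when its lens is removed, exchanged or repositioned for rotation between months 18 and 24; the fellow-eye substitution in 7.4 is a smaller part of the same gap

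*Combined protocol and SAP*

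**What the plan says.** All references are to the combined protocol and SAP.

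- **Endpoint (7.2.1).** "The primary endpoint for this study is rotation of less than or equal to five degrees between 18 and 24 months postoperative". The success criterion refers to treated eyes: "The endpoint will be met if at least 90% of the treated" eyes stay within that limit. Secondary lens surgery is not mentioned.
- **Choice of eye (3.1).** The primary eye is fixed by rule before surgery. When both eyes qualify and surgery is wanted in both, "the eye with the greater magnitude of manifest refraction cylinder will be designated as the primary eye"; if the cylinders are equal, it is the right eye.
- **Substitution (7.4).** If a primary eye "is explanted during the study, the enrolled fellow eye of that subject may be used in its place for the primary analysis". The only condition is that the fellow eye was enrolled and implanted. No reason or time for the explant is specified, and no decision-maker or decision date is named.
- **Test (7.5).** The null is rejected if the upper limit of the two-sided 95% exact binomial interval for the failure proportion is at most 0.1. Explants are not mentioned.
- **Missing data (7.6).** Missing endpoints are multiply imputed for the ITT analysis: "The method, seed number, number of datasets generated, and predictors to be used will be specified in advance of data lock". In addition, "Sensitivity analyses will be performed using an imputation of failure (worst case) for all missing", with a best case and, if the two disagree, a tipping-point analysis.
- **Lens surgery elsewhere.** Section 6.3.1 requires expedited reporting of "all secondary surgical interventions (removal, replacement or repositioning) involving the study lens". Section 3.2.3 has one visit rule specific to explantation: "If both TICL lenses are explanted, a minimum of one post-explant visit should be completed to record safety measures for the subject". Neither affects how the endpoint is scored.

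**The concern.** A lens that turns more than 5 degrees after the month-18 image and is operated on for that reason is exactly what the endpoint is meant to detect. The plan leaves three routes by which it may not be counted:

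- **Removed, fellow eye used.** The analysed value comes from an eye that did not have the event. Where the two eyes differ in cylinder, it is the eye with less.
- **Removed, no fellow eye used.** The month-24 value is missing and is imputed, most often as a success when few eyes fail.
- **Repositioned or exchanged.** The substitution clause is not triggered by repositioning, and 7.4 does not say whether an exchange counts as an explant. A month-24 image may exist, but it shows where the lens lay after the second operation.

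All three routes favour success. The word *may* in 7.4 also leaves a choice open in an open-label study, although 7.6 fixes the imputation details before data lock. The stake is the study's only effectiveness hypothesis test; the secondary endpoints have no performance targets.

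**Working it through.** **Inputs.** Performance limit 10%, assumed failure rate 2%, 100 evaluable eyes, stated power 94.9%, losses of 10% per year and 124 primary eyes enrolled (7.1, 7.4); exact two-sided 95% interval (7.5). The rate of secondary surgery for rotation is not given and is varied below as an assumption.

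**1. Reproduce the plan's figures.** The exact upper limit for x failures in n eyes is the 0.975 quantile of Beta(x+1, n−x).

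| Failures / eyes | Upper limit | Result |
|---|---|---|
| 4/100 | 0.0993 | pass |
| 5/100 | 0.1128 | fail |
| 5/124 | 0.0916 | pass |
| 6/124 | 0.1023 | fail |

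The test therefore passes with at most 4 failures in 100. P(X ≤ 4 | 100, 0.02) = 0.9492, which matches the stated 94.9%. Enrolment also matches: 100/0.9² = 123.5, so 124. The table shows that at the boundary one uncounted failure reverses the conclusion.

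**2. False-pass chance at a true failure rate of 10%.** With every failure counted, P(X ≤ 4 | 100, 0.10) = 0.0237 and P(X ≤ 5 | 124, 0.10) = 0.0122. Now let a share e of all primary eyes be rotation failures explanted after month 18.

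- *Swapped*, with fellow eyes failing at rate f: counted rate = 0.10 − e + f·e.
- *Left missing and imputed at the observed rate*: counted rate = (0.10 − e)/(1 − e), treated as if n were fully observed. This approximates multiple imputation and ignores its added variance.

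| e (assumed) | n | Swapped, f = 10% to f = 2% | Imputed |
|---|---|---|---|
| 1% | 100 | 4.43% to 4.68% | 4.46% |
| 2% | 100 | 7.97% to 8.81% | 8.16% |
| 1% | 124 | 2.62% to 2.80% | 2.64% |
| 2% | 124 | 5.36% to 6.05% | 5.51% |

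At e = 0 there is no inflation. The 2% row is an extreme, because it equals the whole planned failure rate. The two right-hand columns are close, so the rise comes from not scoring the eye as a failure; how the gap is then filled matters little.

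**3. Tipping point.** 124 × 0.81 = 100.4, so about 24 eyes are missing under the plan's own attrition. Even with no other failures, 24/124 has an upper limit of 0.274, so the worst case fails. If the best case passes, the tipping-point analysis runs. The conclusion changes at 6 failures in 124. Suppose the other 100 eyes include 3 true failures, one of them explanted for rotation after month 18:

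| Handling of that eye | Observed failures | Missing eyes | Tips at |
|---|---|---|---|
| Scored as a failure | 3 of 100 | 24 | 3 of 24 (12.5%) |
| Left missing (7.6) | 2 of 99 | 25 | 4 of 25 (16.0%) |
| Swapped for a success (7.4) | 2 of 100 | 24 | 4 of 24 (16.7%) |

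The step from 3 to 4 comes from the missing failure rule. The swap alone moves the tipping point only from 16.0% to 16.7%.

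**The case against.** The strongest objection is that the route is narrow. An explanted failure is replaced only if rotation beyond 5 degrees first arises after month 18, the lens is removed, no usable image precedes removal, an implanted fellow eye has its own results, and someone chooses to substitute. The plan expects at most 2% of eyes to rotate that far, about 2 in 100, and gives no explant rate. This stands: the expected number of such eyes may be zero. It limits the size of the problem and leaves the gap in the rule, and the repositioning route needs neither an explant nor a fellow eye.

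A second objection is that the plan partly covers the case. An image taken before removal could be recorded at an unscheduled visit with its intended visit identified (5.1.5), and 7.5 evaluates out-of-window data and pools them if justified. An eye imaged that way has a measured outcome. This also stands in part, but no such image is required, and 7.4 would still permit replacing the eye.

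Third, a reader might infer that the substitution clause is the main source of bias, or that it defeats the sensitivity analyses. The documents do not support that. A swapped eye does leave the set varied in 7.6, but the tipping count is 4 either way and the false-pass chance is nearly the same as with imputation. If fellow eyes fail at 10%, the swap gives a slightly lower false-pass chance than imputation (4.43% against 4.46% at e = 1%, 100 eyes). Nor is the event hidden: the explant stays visible in safety reporting under 6.3.1.

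Finally, the clause preserves evaluable eyes. That is a real purpose, and its cost is counted under the fix.

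**Conclusion.** The concern holds as a missing scoring rule. As written, a primary eye that fails by rotation after month 18 and has secondary lens surgery for it before the month-24 image can be counted as a success or imputed. The absence of the rule can be read directly from 7.2.1 to 7.6, and confidence in it is high.

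Confidence in the size is low. A single eye matters only near the boundary (4 against 5 failures in 100, or 5 against 6 in 124). If 1% of primary eyes were such cases, the false-pass chance would rise from 2.4% to about 4.5% with 100 eyes, and from 1.2% to about 2.6–2.8% with 124. These figures assume a true failure rate at the 10% limit, and they fall to no inflation if no lens is operated on for rotation in the interval. The documents do not support a claim that the result will be biased, only that the plan permits it. The point should be fixed because the correction is short and every route errs towards success.

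**What to change.** Analysis text only:

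1. **7.2.1 and 7.5.** Score a primary eye as a failure if its lens is explanted, exchanged or repositioned for rotation arising between the month-18 and month-24 assessments. Where an image before the secondary surgery exists, apply the reading center's measurement against the 5-degree limit; where none exists, count the eye as a failure.
2. **7.4.** Keep the pre-designated primary eye in the primary analysis. Treat explants for other reasons as missing under 7.6, so that the worst-case and tipping-point analyses include them.
3. **7.4 and 7.6.** Keep fellow-eye substitution only as a labelled sensitivity analysis that lists each substituted eye with the date and reason for explantation.

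**Cost.** A few sentences, slightly fewer observed eyes and possibly a less favourable estimate. Where no pre-surgery image exists, an eye that rotated 5 degrees or less could be counted as a failure. Planned power with 100 eyes stays at 94.9%, because the assumed 2% is the rotational failure rate among all eyes and already includes these cases.

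A reader might infer that power is safe in every analysis. It is not, because the margin is thin (124 × 0.81 = 100.4). In an observed-eye analysis such as the PP set, 99 eyes would allow only 3 failures, since 4/99 gives 0.1002, and P(X ≤ 3 | 99, 0.02) is 86.3%. The ITT analysis imputes and does not lose eyes in this way.

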7.5 Statistical Analysis

The two-sided 95.0% upper confidence limit of the proportion of eyes with $>5^\circ$ absolute rotation will be calculated. The null hypothesis will be rejected if the two-sided 95.0% upper confidence limit of the proportion of eyes with $>5^\circ$ absolute rotation between 18 and 24 months is ≤ 0.1 . An exact binomial confidence interval will be used.

Secondary endpoints, degrees of rotation between visits and misalignment from the intended orientation will be analyzed using descriptive statistics. Rates of rotation of the TICL of <10 , <20 and <30 degrees from the intended orientation will be reported.

Evaluation of study endpoints will be conducted separately for study visits conducted within the protocol defined visit windows and separately for those outside of the visit windows. Out of window visits will be identified during analysis of study accountability. If separate evaluations of in-window and out-of-window data, including the distribution of times outside of the window that data were collected, justify poolability, then the endpoints will be analyzed using the pooled data.

To verify poolability of data across sites, outcomes for the primary endpoint by site will be compared using a 0.15 alpha to test for differences in the primary endpoint among sites. If differences are found, data will be summarized separately by site and possible reasons for the finding will be investigated.

To allow for 10% attrition annually, a total of 124 subjects (up to 248 eyes, with 124 being primary) will be enrolled for assessment of the primary and secondary effectiveness/safety endpoints.

7.6 Missing Data Imputation

Missing primary effectiveness endpoint data will be imputed for the primary effectiveness analysis when using the ITT analysis population. The primary method used will be by multiple imputation using SAS PROC MI and MIANALIZE. The method, seed number, number of datasets generated, and predictors to be used will be specified in advance of data lock. Sensitivity analyses will be performed using an imputation of failure (worst case) for all missing and again with an imputation of success for all missing (best case). If the results of the two extreme imputation methods differ in the conclusion drawn, a tipping point analysis will be performed to determine the point at which significance tips.

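### The plan does not say which pooled upper limit is compared with 0.10 in the primary ITT analysis; with 100 of 124 eyes observed, that choice moves the one-sided error between about 1% and 6%

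*Combined protocol and SAP*

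**What the plan says.** Section 7.5 sets the decision rule: "The null hypothesis will be rejected if the two-sided 95.0% upper confidence limit of the proportion of eyes with" more than 5° absolute rotation between months 18 and 24 is at most 0.1. It adds "An exact binomial confidence interval will be used".

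Section 7.6 covers missing endpoints: "Missing primary effectiveness endpoint data will be imputed for the primary effectiveness analysis when using the ITT analysis population". On the tool it says "The primary method used will be by multiple imputation using SAS PROC MI and MIANALIZE" (the second name is read here as MIANALYZE). Some details come later: "The method, seed number, number of datasets generated, and predictors to be used will be specified in advance of data lock". Worst-case and best-case imputations are sensitivity analyses, with a tipping-point analysis if the two disagree.

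Section 7.3 ranks the populations: "The PP analysis set will be supportive of the ITT findings". Section 7.4 gives 94.9% power with 100 eyes at a failure rate of 2% or less, and plans for attrition: "To allow for losses of 10% per year, a total of up to 124 primary eyes of 124 subjects will be enrolled".

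**The concern.** An exact binomial limit needs one whole-number count out of one sample size. Multiple imputation gives several completed datasets with different counts. MIANALYZE combines their estimates and standard errors as estimate plus t times standard error. That is not an exact binomial limit, and its value depends on the scale on which estimates are pooled. Sections 7.5 and 7.6 therefore do not together define one number to compare with 0.10.

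Missing endpoints are the planned case, so the gap affects the study's only hypothesis test. For results near the boundary, pass or fail could turn on the pooling scale and the number of imputations, neither of which is fixed.

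**Working it through.** **Inputs.** Criterion, interval type and two-sided 95% level: Section 7.5. 10% boundary: Section 7.1. 2% assumed rate, 100 eyes, 124 enrolled, 10% loss per year: Section 7.4. Assumptions not in the documents: missing completely at random; imputation without predictors; M = 5 to 100 datasets.

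**1. The plan's own figures.** Expected observed eyes: 124 × 0.9 × 0.9 = 100.4. With n = 100, the exact (Clopper-Pearson) upper limit is 0.0993 at 4 failures and 0.1128 at 5, so success means at most 4.
- Power: P(X ≤ 4 | 0.02) = 0.9492, which reproduces 94.9%.
- Error: P(X ≤ 4 | 0.10) = 0.0237.

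**2. One raw-scale limit by hand: 5 failures in 100 observed, 24 missing, M = 20.** Take the pooled proportion Q as 0.05 and the between-imputation variance B at its approximate expected value.
- Within: U = 0.05 × 0.95 / 124 = 0.000383.
- Between: B = (24/124)² × 0.0475 × (1/24 + 1/100) = 0.0000919.
- Total: T = U + (1 + 1/20) × B = 0.000480; square root 0.0219.
- Degrees of freedom about 469, t = 1.965. Limit = 0.05 + 1.965 × 0.0219 = 0.093: pass.

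At 6 failures the same steps give 0.107: fail. So raw pooling passes at about 5 failures, where the exact rule stops at 4. P(X ≤ 5 | 100, 0.10) = 0.0576, which is where the 5-6% comes from.

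**3. Simulation of the whole procedure.** 124 eyes; the failure rate is drawn from its beta posterior given the observed eyes; Rubin's rules with a t limit.

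| Pooled limit, 100 observed | Error at a true 10% rate | Power at 2% |
|---|---|---|
| Raw proportion | about 5-6% | not the issue |
| Logit | about 1-2% | about 82-90% |
| Clopper-Pearson at effective n, or Wilson-type MI | 1.1-1.9% | 86-91% |

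Over 90 to 118 observed eyes and M = 5 to 100, raw pooling gives roughly 4-7%, above 2.5% throughout. With exactly 5 failures in 100 observed eyes it passes in about 75% of runs at M = 5, 84-95% at M = 20 and nearly all at M = 100.

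**4. Source of the inflation.** With complete data on 124 eyes, the raw-scale limit is 0.0971 at 7 failures and 0.1078 at 8, so it passes up to 7 (error 6.3%). The exact limit is 0.0916 at 5 and 0.1023 at 6, so it passes up to 5 (error 1.2%). The raw scale causes the excess, not the assumed missingness.

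**5. Averaging the exact limits of the imputed datasets.** Error is close to 2.5% with 100 observed eyes but about 3-4% with 90 to 94. The average also ignores between-imputation variance, and MIANALYZE does not produce it.

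**6. Whether the sensitivity analyses settle it.** With 24 missing, best-case and worst-case exact limits are 0.0805 and 0.310 at 4 observed failures, and 0.0916 and 0.318 at 5. Best case passes and worst case fails at both counts, so they do not separate the contested results.

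**The case against.** The strongest reply is that this is missing detail, not a conflict. Section 7.5 fixes the interval type, and Section 7.6 defers the method to before data lock, which may be meant to include pooling. The sections could be reconciled, for instance by averaging exact limits. In part this stands: the gap can be closed in a step already planned. But the deferral does not expressly list the pooled limit or its scale, and averaging exact limits is not reliably calibrated (step 5).

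Second, a reader might infer that the trial will run at about twice its nominal error. The documents do not support that. Nothing in them calls for raw-proportion pooling, and a limit of that type would contradict the exact-interval sentence in Section 7.5. MIANALYZE combines whatever estimates it is given, and on the logit scale the error falls below nominal.

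Third, the two rules also disagree at true rates of 2% to 5%, and a reader might count that as harm. It is not: there the alternative is true and passing is correct.

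Fourth, the simulation is not the plan's analysis. Section 7.6 foresees predictors, and Section 7.4 lets an enrolled fellow eye replace an explanted primary eye. The exact percentages could shift.

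Fifth, there are safeguards. The worst case fails with 6 or more missing eyes even with no observed failures (6/124 gives 0.1023), so at planned attrition any best-case pass triggers the tipping-point analysis. The PP set excludes missing endpoints, so the exact rule applies to it directly. These would expose a fragile pass, but neither is the primary decision.

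**Conclusion.** The concern holds as a gap in the primary decision rule and should be fixed. Section 7.5 requires an exact binomial limit, Section 7.6 names a procedure that does not return one, and the limit compared with 0.10 is unstated. With 100 of 124 eyes observed, the one-sided error at a true 10% rate is about 5-6% for raw pooling and about 1-2% for logit pooling, against 2.5% nominal. Across 90 to 118 observed eyes and M = 5 to 100, the raw-scale figure is roughly 4-7%. All of this rests on data missing completely at random and imputation without predictors.

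A reader might also infer that the 94.9% power is wrong or that the study is too small. Neither follows: 94.9% is correct for the exact test on 100 fully observed eyes. The remedy is a clarification before data lock, and the design, sample size and criterion need not change.

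**What to change.** - In Section 7.6, before data lock, state that the raw-scale MIANALYZE limit will not be used, and name one pooled upper limit suited to small proportions. One option is a Clopper-Pearson limit at effective sample size Q(1 − Q)/T (Q the pooled proportion, T the total variance), with a stated convention when Q = 0, such as the number of observed eyes. In the step 2 example this size is 0.0475 / 0.000480 = 99, and the limit is 0.113, agreeing with the exact rule. Another option is a Wilson-type MI interval.
- Confirm by simulation that the one-sided error is at most 2.5% at a true 10% rate over the expected range of missingness.
- Refer from Section 7.5 to that rule and keep the criterion of at most 0.10.
- In Section 7.4, label 94.9% as the power of the exact test on 100 fully observed eyes.

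The cost is a few sentences, some programming and one simulation, within the pre-lock step that Section 7.6 already schedules. There is also a power cost if attrition is as planned: about 86-91% at a 2% rate with 24 eyes missing, against 94.9%, and less if more eyes are lost. With 112 observed, power is 93-95%, against 92.5% for the exact rule on those eyes; with 118 it is 96-97%, against 96.8%. So there is little or no loss at about 112 or more observed.
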